10.1.1. Definition of Analyzed Study Populations

The following study populations will be considered when reporting study results:

- The study population for safety includes all patients receiving at least a portion of 1 dose of study drug (Abemaciclib).
- The study population for efficacy will include all safety population patients who have baseline and follow-up tumor measurements as required for assessment by iRECIST.

Only those patients who are deemed ineligible (e.g., do not satisfy eligibility criteria) or who receive no study drug (i.e., no Abemaciclib) will be eliminated from the analysis. Ineligible patients who receive therapy will not be included in the assessment of efficacy endpoints, but their data will be included in the assessment of all AE reporting.

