Given the role of CDK4/6 in tumor resistance to endocrine therapy, in activation of the DNA damage response, and in promoting radiation resistance, we hypothesize that the targeting of CDK4/6 with abemaciclib will enhance the cytotoxicity in combination with blockade of the androgen receptor pathway.

Objectives:

Primary:

- To assess clinical response rates using
 - Proportion of patients with PSA nadir of ≤ 0.5 ng/ml on treatment

Secondary:

- Proportion of patients with PSA declines prior to radiotherapy
- Time to PSA failure
- To study the tolerability and feasibility of combining abemaciclib with androgen deprivation therapy (ADT) for localized high-risk or locally advanced prostate cancer.

Exploratory:

- MRI-US fusion imaging pre-treatment and at 6 months post RT with comparison with historical controls receiving RT + ADT
- Baseline (mandatory) and 6 months (optional) post RT tumor tissue profiling (MRI-US fusion guided) to identify association of molecular profile with PSA decline at 1 year
- Baseline, pre-radiotherapy, and 6 months post-RT blood collection and profiling for molecular analysis

Methodology:

Abemaciclib at 150 mg PO BID, ADT by administering LHRH analogues (goserelin, leuprolide, etc), and radiation therapy in conjunction with ADT

Overall design:

A single institution (UAB) phase II trial is proposed to evaluate the clinical and radiologic response as well as safety and tolerability of abemaciclib in combination with ADT neoadjuvantly and adjuvantly for patients with high-risk localized or locally advanced prostate cancer who will receive

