definitive RT+ADT. Simon's optimal two-stage design (Simon, 1989) will be used for conducting the trial. The null hypothesis is that the proportion of patients with PSA <0.5 without any treatment is 5%, and the alternative hypothesis is that the proportion of patient with PSA <0.5 at 6 weeks into treatment is 30% or higher. The trial is carried out in two stages. In stage I, a total number of 5 patients is accrued. If there are 0 response (PSA < 0.5) among these 5 patients, the study will be early stopped. Otherwise, additional 18 patients will be accrued in stage II, resulting in a total number sample size of 23. If there are 4 or more responses (PSA < 0.5) among these 23 patients, we reject the null hypothesis and claim that the treatment is promising. The design controls the type I error rate at one-sided 0.025 and yields the power of 80%. If we reject the null hypothesis, seven additional patients will be enrolled to explore the association between biomarkers and clinical activities. Patients receive ADT x 2 years and will start 3 months before RT. Abemaciclib will start with initiation of ADT and pause 2 weeks prior to start of RT. Abemaciclib will resume with the first ADT administration post-radiation, which typically is at 1 month post radiation therapy. Abemaciclib and ADT will continue for a total ADT period of 24 months. Patients will have laboratory evaluation every 2 weeks for the first 2 months and monthly thereafter for the next 2 months. Patients are also seen and evaluated every 4 weeks with laboratory evaluation. Labs may be drawn at outside laboratories at the PI's discretion. For toxicity or adverse event, patients will undergo labs, physical examination and grades of toxicities will be determined using NCI CTCAE version 4.03. Disease response and biochemical failure will be assessed by PSA prior to the start of radiation and every 3 months following the end of radiotherapy and by the investigator (physical exam). The determination of disease progression for the study requires a confirmation of 3 consecutive rises of PSA 3 months apart in the setting of testosterone recovery. Patients will be withdrawn from study for following toxicities,

Toxicity Category	Drug-Related Toxicity/Grade
Hematologic	Grade 4 neutropenia for ≥ 5 days
	Febrile neutropenia: ANC < 1000/mm ³ with a single temperature of $>38.3^{\circ}\text{C}$ (101°F) or a sustained temperature of $\geq 38^{\circ}\text{C}$ (100.4°F) for more than one hour.

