2.6. Potential Risks and Benefits to Human Patients

2.6.1. Potential Risks

Abemaciclib

Based on clinical experience with abemaciclib, the adverse events of special interest (AESIs) are neutropenia, infections, diarrhea, blood creatinine increased, hepatic events (increases in aspartate aminotransferase [AST] and alanine aminotransferase [ALT]), and embolism (mainly pulmonary embolism and deep vein thrombosis); furthermore, interstitial lung disease/pneumonitis is considered an adverse event (AE) of note.

Computed Tomography (CT) Scans

Patients will be exposed to a relatively small amount of radiation as a result of the CT scans required in this study. This degree of exposure has not been associated with harmful health effects. In addition, the frequency of CT scans performed in this study is similar to the standard of care frequency. Patients with a medical contraindication to CT scans or known iodinated contrast allergies may instead undergo magnetic resonance imaging (MRI). There is minimal risk of MRI imaging in patients able to undergo this type of exam including very rare reports of gadolinium-induce nephrogenic systemic fibrosis in patients with poor renal function.

MRI-US imaging.

Patients will undergo MRI-US fusion imaging pre-treatment and at 6 months post RT with comparison with historical controls receiving RT + ADT. There is minimal risk of MRI imaging in patients able to undergo this type of exam including very rare reports of gadolinium-induce nephrogenic systemic fibrosis in patients with poor renal function.

Prostate biopsy

Patients will have undergone MRI-US guided biopsy of the prostate at the time of diagnosis and archived tumor tissue will be used at screening for baseline analysis. An optional biopsy will be scheduled at 6 months post RT for tumor tissue profiling to identify association of molecular profile with PSA decline at 1 year. Risks include but are not limited to bleeding from biopsy site, increased risk of infection and complications related to anesthesia for the procedure.

Venipuncture

Patients could also experience side effects from venipuncture for tests that will be done as part of this study, including pain, tenderness, and bruising at the site of collection, and rarely infection may occur at the spot where the needle is inserted.

Other Risks

This study treatment may involve risks to unborn children and therefore patients should not father a baby while participating in this study.

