- b. BID PO dosing Abemaciclib. Abemaciclib will be stopped 2 weeks before RT and will be resumed 1 month after RT.
- c. LHRH analogues will be administered on C1D1 and continued every 3 months for a maximum of 24 months.
- d. An optional MRI-TRUS guided biopsy will be performed at 6 months post radiotherapy,
- e. Radiotherapy will be started after 3 months of start of abemaciclib and ADT.
- f. CT scan or MRI scan will be done to rule out metastatic disease (within 3 months). It will be conducted again at the time of PSA rise (biochemical failure).
- g. Abemaciclib will be stopped 2 weeks before scheduled RT. It will be administered for half a cycle in cycle 3.

- h. Abemaciclib and ADT will be resumed after 1 month of completing RT. This will be counted as 4th cycle and future cycles will continue monthly for Abemaciclib. ADT will be given quarterly. Study treatment will continue until patient progresses, has toxicities or withdraws from study.
- i. Laboratory Studies: The first 2 cycles, labs will be drawn every 2 weeks and may be drawn at outside lab at the PI's discretion.

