 - Where possible, the visible portion of the nodal PTV should also be assessed to ensure that the associated vessels fall within the target volumes. Note that field-of-view limitations may impair ability to visualize upper aspect of the pelvis with CBCT, depending on isocenter placement
- For men receiving post-prostatectomy RT the focus of alignment will be at the anterior rectal wall at the level of the VUA (vesicoureteral anastomosis)
- Alignment to implanted fiducial markers may be used instead of daily CBCT
 - Weekly CBCT is strongly recommended to assess soft tissue anatomy and bladder and rectal filling.

Follow up

Disease monitoring	PSA every 3 months for first year and then every 6-12 months thereafter. First follow-up PSA should not be drawn sooner than 3 months post-radiation DRE if PSA is detectable and not actively declining
Androgen suppression monitoring (if applicable)	Bone density monitoring Consider repeating testosterone profile 6-12 months after initiating androgen suppression for men receiving long term therapy
Late toxicity evaluation	IPSS at each visit SHIM at each visit CTCAE assessed lower GI toxicity CTCAE assessed GU toxicity
Imaging	Not routinely indicated

Contributing authors

- [name], PhD (Site Leader)
- [name] (First Author)
- M. [name], PhD
- D. [name]
- [name]
- [name]
- [name], CMD
- [name], RT(R,T)
- [name], RT(R,T,CT)

References

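### Section 10.1.1 limits the efficacy population to patients with follow-up iRECIST measurements, which no primary or secondary endpoint uses and no section routinely schedules, against its own next paragraph and the 5 and 23 patients of the Simon rule

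*Combined protocol and SAP*

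**What the plan says.** Section 10.1.1 opens with "The following study populations will be considered when reporting study results" and then defines the efficacy population as "all safety population patients who have baseline and follow-up tumor measurements as required for assessment by iRECIST". Its next paragraph gives a different exclusion rule: "Only those patients who are deemed ineligible (e.g., do not satisfy eligibility criteria) or who receive no study drug" are to be removed from the analysis. A missing scan is not among the reasons.

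The endpoints do not involve tumour measurement. The primary endpoint is the proportion reaching a PSA nadir of 0.5 ng/ml or less (Sections 3 and 10.2.1). The secondary efficacy endpoints are PSA decline before radiotherapy and time to PSA failure (Sections 3 and 10.2.2), and the remaining secondary objective is tolerability and feasibility. Disease progression "requires a confirmation of 3 consecutive rises of PSA 3 months apart in the setting of testosterone recovery" (Synopsis). Outside Section 10.1.1, iRECIST appears only in the abbreviation list.

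On imaging:

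- Table 2, footnote f, has CT or MRI at screening and then: "It will be conducted again at the time of PSA rise (biochemical failure".
- The Synopsis describes a trial "to evaluate the clinical and radiologic response as well as safety and tolerability of abemaciclib" but sets no schedule for radiologic response.
- Section 2.6.1 says "the frequency of CT scans performed in this study is similar to the standard of care frequency". The institutional guideline in Appendix 3 gives follow-up imaging as "Not routinely indicated"; that guideline covers clinically localized disease and not node-positive disease, which this trial admits.
- Section 4.1.3 asks for best-effort radiographic monitoring after discontinuation without progression.
- MRI-US fusion imaging 6 months after radiotherapy is an exploratory objective and is not described as an iRECIST assessment.

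Sections 10.1, 10.2 and 10.2.1 apply the Simon rule to patients accrued: stop at 0 responses in 5, claim success at 4 or more in 23. Sections 10.2 and 10.2.1 add a point estimate with two-sided 95% limits.

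**The concern.** An eligible, treated patient with complete PSA data but no follow-up scan is outside the efficacy population under the bullet and inside it under the next paragraph. Nothing ranks the two statements. Entry under the bullet also depends on something that happens after treatment starts, and the scheduled trigger for a repeat scan is PSA itself, the variable that defines the endpoint.

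The stakes depend on how far the bullet reaches. On the narrower reading, which the lead-in favours, it governs reporting only. The decision then uses 5 and 23 patients, while the published rate and its limits use whoever was scanned, and the two can disagree. On the wider reading it also governs the decision, and few or none of the first 5 may be evaluable at stage I. At the 6-week time point of Sections 10.1 and 10.2, radiotherapy, planned at 3 months, has not begun. If footnote f's biochemical failure is the Synopsis progression rule, it needs three rises 3 months apart with testosterone recovery, while ADT runs for 24 months. In an open-label single-arm trial, choosing between the denominators once PSA results are known would be a post hoc choice of the primary analysis set.

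**Working it through.** **Inputs from Section 10.1.** Null rate 5%, alternative 30%, stage I of 5 (stop at 0), total 23, success at 4 or more, one-sided type I error 0.025, power 80%.

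**The plan's own figure.** With X1 ~ Bin(5, p) and X2 ~ Bin(18, p), P(success) is the sum over x = 1 to 5 of P(X1 = x) × P(X2 ≥ 4 − x).

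- p = 0.30: 0.3386 + 0.3043 + 0.1321 + 0.0284 + 0.0024 = 0.8057.
- p = 0.05: 0.0118 + 0.0049 + 0.0007 + less than 0.0001 = 0.0174.

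The stated design is reproduced, provided every accrued patient is counted.

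**Evaluability.** The documents give no rate of follow-up tumour measurement. Every rate below is assumed, for illustration.

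**A. Bullet governs reporting only, true rate 30%.** The expected reported rate is (evaluable responders) / (all evaluable).

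- 80% of non-responders and all responders evaluable: 0.30 / (0.30 + 0.70 × 0.8) = 0.349.
- 80% of responders and all non-responders evaluable: 0.24 / (0.24 + 0.70) = 0.255.
- Precision (Clopper-Pearson): 7/23 = 30.4%, limits 13.2% to 52.9%; 3/10 = 30%, limits 6.7% to 65.2%.

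**B. Bullet also governs the decision, no replacement, cut-off of 4 kept.**

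| Assumed loss | Power at 30% | Type I error at 5% |
|---|---|---|
| None | 0.806 | 0.0174 |
| Independent of outcome: 5 in stage I, 20 in total evaluable | 0.775 | 0.0117 |
| Independent of outcome: 4 in stage I, 22 in total evaluable | 0.731 | 0.0133 |
| 80% of responders evaluable (p becomes 0.24 and 0.04) | 0.671 | 0.0083 |
| Only non-responders lost | 0.806 | 0.0174 |

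Evaluable responders are a subset of responders, so without replacement the type I error cannot exceed 0.0174.

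**C. Bullet also governs the decision, accrual continued to 5 and 23 evaluable.** If a fraction e of non-responders and all responders are evaluable, the rate among evaluable patients is p′ = p / (p + (1 − p)e). At p = 0.05:

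- e = 0.8: p′ = 0.05 / 0.81 = 0.0617, type I error 0.034.
- e = 0.7: p′ = 0.05 / 0.715 = 0.0699, type I error 0.050.
- The type I error reaches 0.025 at e of about 0.89.

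If instead 80% of responders and all non-responders are evaluable, p′ = 0.24 / 0.94 = 0.2553 and 0.04 / 0.99 = 0.0404, giving power 0.712 and type I error 0.0085.

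**The case against.** The best counter-argument is about reach. The lead-in ties these populations to reporting, and every statement of the Simon rule counts accrued patients by PSA without mentioning an efficacy population. On that reading the rule is untouched, and all the power and type I error figures in B and C fall away. C also needs a replacement rule the documents do not contain, and it needs non-responders to be scanned less often, whereas a scan triggered by a PSA rise would, if anything, pick out patients doing badly. The stage I argument leans on the 6-week read-out, while Section 10.2.1 uses the nadir during treatment, which leaves more time for scans. Section 2.6.1 plans MRI-US fusion imaging for all patients 6 months after radiotherapy, and the Appendix 3 guideline describes itself as a general reference. Finally, the bullet looks like template text, and deleting it would by itself remove the contradiction.

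Much of this stands. The effect on the decision rule is conditional, the rates are assumed, and the power and type I error scenarios cannot carry the finding. What remains does not depend on them. The bullet is the only item labelled as the efficacy population, the next paragraph contradicts it, and following it as written puts the reported response rate on a set selected after treatment began. Unscheduled scans and exploratory MRI do not make iRECIST follow-up a routine assessment.

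**Conclusion.** The concern holds and the text must be corrected. The contradiction is plain in the documents and needs no assumption. The Simon arithmetic is right; the population definition is wrong.

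The size is not determinable from the documents. On the narrower reading, the illustrations shift the expected reported rate from 30% to 34.9% or 25.5% and widen the limits. On the wider reading without replacement, the illustrated losses leave power between 0.671 and 0.806, with no inflation of type I error. Type I error above 0.025 requires the wider reading, replacement of unevaluable patients, and fewer than about 89% of non-responders evaluable with all responders evaluable. The direction of bias cannot be fixed, since scans at PSA rise, best-effort scans and later failure among responders pull in different directions.

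**What to change.** Replace the iRECIST bullet in Section 10.1.1 with wording such as:

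> Efficacy analyses include every eligible patient who took any part of one abemaciclib dose. The 0-of-5 and 4-of-23 rules apply to the first 5 and first 23 such patients by order of enrolment. The primary estimate and its two-sided 95% limits use those same 23. The seven expansion patients are reported separately. A patient with no qualifying PSA counts as a non-responder.

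The population comes from the section's own second paragraph. Counting missing PSA as non-response and reporting the seven patients separately are recommendations that the documents do not dictate. Any iRECIST summary the sponsor wishes to keep should be a separate exploratory set. The PSA time point (6 weeks or nadir during treatment) must be settled before a qualifying PSA can be defined; that, and the purpose of the target-lesion inclusion criterion, are separate points to reconcile.

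Costs:

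- **Enrolment.** Ineligible or untreated patients would be replaced to reach 23. The 33 recruits allow only for 10% screen failure, so each replacement may need one more patient.
- **Missing PSA counts against the drug.** If 10% is missing independently of outcome (assumed), p becomes 0.27 and 0.045, giving power 0.747 and type I error 0.0123; if 20%, p becomes 0.24 and 0.04, giving 0.671 and 0.0083.
- **Precision.** Keeping the 23 apart from the seven gives limits of 13.2% to 52.9% for 7/23, against 14.7% to 49.4% for 9/30.

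The gain is one denominator for the decision and the reported rate that does not depend on who was scanned.

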10.2. Data Analysis

Simon's optimal two-stage design (Simon, 1989) will be used for conducting the trial. The null hypothesis is that the proportion of patient with PSA <0.5 without treatment is 5%, and the alternative hypothesis is that the proportion of patient with PSA <0.5 at 6 weeks into treatment is 30% or higher. The trial is carried out in two stages. In stage I, a total number of 5 patients is accrued. If there are 0 response (PSA < 0.5) among these 5 patients, the study will be early stopped. Otherwise, additional 18 patients will be accrued in stage II, resulting in a total number sample size of 23. If there are 4 or more responses (PSA < 0.5) among these 23 patients, we reject the null hypothesis and claim that the treatment is promising. The design controls the type I error rate at one-sided 0.025 and yields the power of 80%. This response rate will be summarized using both a point estimate and its 2-sided 95% confidence limits. If we reject the null hypothesis, seven additional patients will be enrolled to explore the association between biomarkers and clinical activities. Descriptive statistics will be used to summarize patient demographics, baseline characteristics, treatment administration/compliance, efficacy, biomarkers, and archival tumor tissue, safety, and efficacy parameters. Time to PSA failure will be analyzed using the Kaplan-Meier method. The assessment of safety data will be based on the summarization of treatment related AEs, SAEs, AEs leading to discontinuation from study treatment or efficacy follow-up, and clinical laboratory tests. Data will also be displayed graphically, where appropriate.

10.2.1. Analysis of Primary Objective

For each patient, PSA will be measured on systemic treatment with Abemaciclib and ADT after radiotherapy. The primary endpoint is percentage of patients who achieve the PSA nadir levels of \leq 0.5 ng/ml during their treatment. Simon's optimal two-stage design (Simon, 1989) will be used for conducting the trial. The null hypothesis is that the proportion of patient with PSA <0.5 is 5%, and the alternative hypothesis is that the proportion of patient with PSA <0.5 is 30% or higher. The trial is carried out in two stages. In stage I, a total number of 5 patients is accrued. If there are 0 response (PSA < 0.5) among these 5 patients, the study will be early stopped. Otherwise, additional 18 patients will be accrued in stage II, resulting in a total number sample size of 23. If there are 4 or more responses (PSA < 0.5) among these 23 patients, we reject the null hypothesis and claim that the treatment is promising. The design controls the type I error rate at one-sided 0.025 and yields the power of 80%. This response rate will be summarized using both a point estimate and its 2-sided 95% confidence limits.

10.2.2. Analysis of Secondary Objective

For each patient, PSA declines prior to radiotherapy- calculated from nadir level prior to initiation of radiation therapy compared from pre-treatment baseline - will be listed. The secondary endpoint will be reported as percentage of patients who achieve a PSA decline prior to radiotherapy with combination treatment of ADT and Abemaciclib compared to their baseline PSA levels. This response rate will be summarized using both a point estimate and its 2-sided 95% confidence limits.

Another secondary endpoint will be time to PSA failure. Time to PSA failure will be analyzed using the Kaplan-Meier method. SAEs (including deaths) will be tabulated. Subject listings of all AEs, SAEs (including deaths), and their attribution will be provided.

All AEs with an onset after initiation of treatment will be considered as treatment-emergent AEs. A preexisting condition that worsens after study drug treatment will also be considered as a treatment-emergent AE. All AEs will be coded by MedDRA SOC and PT.

The number and percentage of patients with the following types of treatment-emergent AEs will be summarized: all AEs, all SAEs, AEs related to study drug ((Abemaciclib), AEs resulting in study drug discontinuation, and clinically significant laboratory abnormalities. Non-treatment-emergent serious AEs will be presented separately from treatment-emergent AEs. Deaths will be reported with demographic information. Laboratory results will be summarized descriptively by dose level. Additional exploratory statistical analysis will be performed as it deemed necessary.

